## **12.5 POST-STUDY ADVERSE EVENTS**

The Sponsor should be notified if the investigator becomes aware of any serious adverse event that occurs after the end of the adverse event reporting period (defined as 28 days after the last dose of study drug), if the event is believed to be related to prior study drug treatment.

The investigator should report these events directly to the Sponsor or its designee, either by faxing or by scanning and emailing the Serious Adverse Event/Adverse Event of Special Interest Reporting Form using the fax number or email address provided to investigators.

## **12.6 EXPEDITED REPORTING TO HEALTH AUTHORITIES, INVESTIGATORS, INSTITUTIONAL REVIEW BOARDS, AND ETHICS COMMITTEES**

The Sponsor will promptly evaluate all serious adverse events and non-serious adverse events of special interest against cumulative product experience to identify and expeditiously communicate possible new safety findings to investigators, IRBs, ECs, and applicable health authorities based on applicable legislation.

To determine reporting requirements for single adverse event cases, the Sponsor will assess the expectedness of these events for the Investigational Medicinal Product (IMP) including GDC-0810 and palbociclib using the *following reference documents*:

- GDC-0810 Investigator's Brochure
- *Ibrance® US Package Insert*

The Sponsor will compare the severity of each event and the cumulative event frequency reported for the study with the severity and frequency reported in the applicable reference document.

Reporting requirements will also be based on the investigator's assessment of causality and seriousness, with allowance for upgrading by the Sponsor as needed.

## **13. PATIENT END OF TREATMENT**

A patient may be discontinued from study treatment at any time if the patient, the Investigator, or the Sponsor feels that it is not in the patient's best interest to continue on study. The following is a list of possible reasons for early discontinuation of study treatment:

- Disease progression (unless there is reasonable evidence of clinical benefit to justify continuation on the protocol—to be discussed with the Sponsor)
- Any other adverse event that cannot be adequately managed with dose modifications, including dose interruption for up to 28 days
- Protocol violation requiring discontinuation of study treatment
- Patient is not compliant with study procedures
- Lost to follow-up
- Patient withdrawal of consent
- Sponsor request for early termination of study

Patients will be followed for at least 28 calendar days after the last dose of study drug. If a patient is withdrawn from treatment due to an adverse event, the patient will be followed until the adverse event has resolved or stabilized as per Section [12.4](#).

## **End of Study**

The end of this study is defined as the date when the last patient, last visit (LPLV) occurs, *GDC-0810 drug supply is exhausted, or when Sponsor decides to stop the study.*

## **14. PROTOCOL VIOLATIONS**

A protocol violation occurs when the patient or Investigator fails to adhere to significant protocol requirements affecting the inclusion, exclusion, patient safety, and primary endpoint criteria. Protocol violations for this study include, but are not limited to, the following:

- Failure to meet inclusion/exclusion criteria
- Dose modifications (e.g., wrong treatment or incorrect dose) that are not within the protocol specifications
- Use of a prohibited concomitant medication
- Any other deviation that presents significant risk or safety concerns to the patient

Failure to comply with GCP guidelines will also result in a protocol violation. The Sponsor, in consultation with the Investigator, will determine if a protocol violation should result in withdrawal of a patient.

When a protocol violation occurs, it will be discussed with the Investigator and appropriate forms detailing the violation will be generated. This form will be signed by representatives from the Sponsor. A copy of the form will be filed in the site's regulatory binder and in the Sponsor's files.

## **15. STATISTICAL METHODS AND CONSIDERATIONS**

The objective of the Phase Ia/Ib dose escalation is to determine the MTD and/or RP2D of GDC-0810, either as single agent or in combination.

If the safety and PK profile seen in Phase Ia is deemed to be favorable, the Phase Ia will be followed by Phase IIa and Phase Ib, where different cohorts of patients will be enrolled to further assess safety, tolerability, preliminary evidence of anti-tumor activity, and exploratory PD markers of response.

### **15.1 PLANNED ANALYSES**

Planned analyses include the analyses of safety, PK, anti-tumor activity, and data from the FES-PET imaging correlative studies.

Due to the exploratory nature of this study, no confirmatory inferential analyses are planned, and no imputation for missing data will be done. Descriptive statistics (such as means, medians, standard deviations, and ranges for continuous data and percentages for categorical data) will be used to summarize patient characteristics, treatment

administration/compliance, safety parameters, pharmacokinetic parameters, anti-tumor activity endpoints, and exploratory biomarkers. Data will also be displayed graphically, where appropriate. Baseline values will be defined as the closest measurement prior to the first dose of study drug, typically those collected during screening. Change from baseline will be defined as (post-baseline value – baseline value). Data will be summarized by phase/stage and dose cohorts.

## **15.2 DETERMINATION OF SAMPLE SIZE**

### **15.2.1 Phase Ia**

The number of patients to be enrolled in Phase Ia will depend upon the observed safety and PK/PD profile, which will determine the number of dose escalations.

The operating characteristics of the dose escalation rules are shown in [Table 11](#) below, which provides the probability of escalation to the next higher dose for each underlying true DLT rate. For example, for a toxicity that occurs in 5% of subjects, there is a greater than 95% probability of escalating. Conversely, for a common toxicity that occurs with a rate of 70%, the probability of escalating is <5%.

**Table 11 Probability of Escalation to the Next Dose**

True Underlying DLT Rate	5%	10%	20%	30%	40%	50%	60%	70%	80%	90%
Probability of Escalating the Dose	97%	91%	71%	49%	31%	17%	8%	3%	1%	0.1%

[Table 12](#) shows the probability of failing to observe toxicity in a sample size of 3 or 6 patients given various true underlying toxicity rates. For example, with 6 patients, the probability of failing to observe toxicity occurring at least 40% of the time is less than 5%.

**Table 12 Probability of Failing to Observe Toxicity**

True Underlying DLT Rate	5%	10%	20%	30%	40%	50%	60%	70%	80%	90%
Probability of Failing to Observe Toxicity, N=3	86%	73%	51%	34%	22%	13%	6.4%	2.7%	0.8%	0.01%
Probability of Failing to Observe Toxicity, N=6	74%	53%	26%	12%	4.7%	1.6%	0.41%	<0.1%	<0.1%	<0.1%

### **15.2.2 Phase IIa**

At the RP2D, a total of approximately 100 patients *have been* enrolled to further assess the safety, tolerability, preliminary evidence of anti-tumor activity, and exploratory PD markers of response of GDC-0810 in 3 distinct patient populations (Cohorts A1 and A2 will be combined for analysis purposes).

A total of 100 patients in Phase IIa will provide a more robust safety profile as well as sample size for preliminary assessment of anti-tumor activity based on clinical benefit rate (CBR) (see [Table 13](#)), defined as the percentage of patients achieving confirmed RECIST v1.1 defined complete response, partial response, and/or stable disease  $\geq 24$  weeks.

In Cohort A, because the presence of ESR1 mutations are associated with poor prognosis, an objective response rate (ORR), defined as the percentage of patients achieving confirmed complete and/or partial responses of at least 15% (5 out of 30 patients) would be considered of more clinical interest than CBR to warrant further development of GDC-0810 in this mutant patient population.

In Cohort B1, the desired observed CBR is 50%, based on historical CBRs of 46% ([Di Leo et al. 2010](#)) and 48% ([Bachelot et al. 2012](#)) for patients with ER+/HER2– advanced breast cancer after prior treatment with aromatase inhibitors.

In Cohort B2, the desired observed CBR is 20%, based on historical CBRs ranging from 18% to 26% for patients with ER+/HER2– advanced breast cancer after prior treatment with fulvestrant ([Baselga et al. 2011](#); [Yardley et al. 2013](#)).

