As of 9 September 2016, 107 patients have been enrolled in the *combined Phase Ib Cohort D1 and Phase IIa* dose-expansion portion of Study GO29642. *Phase IIa* investigated GDC-0810 at the RP2D of 600 mg QD administered within 30 minutes after a meal. *Phase Ib Cohort D1* investigated 600 mg of GDC-0810 in combination with a luteinizing hormone-releasing hormone (LHRH) agonist. Six patients were enrolled in Cohort D1, thus the 107 patients are predominantly from the *Phase IIa* portion of Study GO29642, Adverse events of any grade related to study drug occurring at >20% frequency in the *Phase IIa* study were diarrhea (44%), nausea (38%), fatigue (36%), and hot flush (21%). Administering GDC-0810 within 30 minutes after a meal may have lowered the incidence of GI toxicities (diarrhea, nausea, vomiting) observed in *Phase IIa*, compared with the *Phase Ib* experience with GI toxicities when GDC-0810 was administered under fasting or non-fasting conditions. Safety data for the *Phase IIa* study remain preliminary with the median treatment duration being 77 days (range 1–547 days).

As of 9 September 2016, 4 patients had been enrolled in the *Phase 1b dose-escalation combination Cohort C1* that examined GDC-0810 at 400 mg in combination with palbociclib at 125 mg. Adverse events of any grade related to study drug occurring at >20% frequency in *Cohort C1* were diarrhea (50%), nausea (75%), fatigue (50%), hot flush (25%), decreased appetite (25%), and gastroesophageal reflux disease (25%). Safety data for *Cohort C1* remain preliminary with a median treatment duration of 134 days (range 56–138 days),

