## 7.2 PHASE IIA

Expansion cohorts consisting of a total of 100 postmenopausal women with locally advanced or metastatic ER+ (HER2-) breast cancer previously treated with an AI will be treated at the RP2D to further characterize the safety, PK, PD, and anti-tumor activity of GDC-0810 as follows:

- **Cohort A:** 30 patients who have confirmed ESR1 mutation of the LBD, further divided into 2 subsets:
  - Cohort A1:** 20 patients who had **no** prior treatment with fulvestrant. FES-PET will be obtained for PD analysis only in Cohort A1.
  - Cohort A2:** 10 patients where prior treatment with fulvestrant is allowed
- **Cohort B:** 70 patients who have progressed following  $\leq 1$  prior therapy with an AI in the advanced/metastatic setting, further divided into 2 subsets:
  - Cohort B1:** 50 patients who had **no** prior treatment with fulvestrant
  - Cohort B2:** 20 patients where prior treatment with fulvestrant is allowed ([Figure 2](#))

[figure not shown]
During the Phase Ib and Phase IIa portion of the study, there will be no PK week lead-in period (i.e., all eligible patients will start continuous daily dosing treatment on Cycle 1 Day 1).

The effect of GDC-0810 on ventricular repolarization will be evaluated in all patients enrolled in the Phase IIa portion of the study.

After enrollment is complete in Cohorts A2, B1, and B2 of the Phase IIa portion of the study, further enrollment in Cohort A1 may be discontinued. *Enrollment in the Phase IIa portion of the study is complete.*

All patients will be treated until disease progression, unacceptable toxicity, or patient withdrawal of consent.

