**Table 13 Two-Sided Confidence Intervals for Phase IIa Cohorts**

Cohort	Sample Size	Assumed Observed Effect	Confidence Level	Two-sided CI
A	N=30	15% ORR	80%	(8.34%, 28.74%)
B1	N=50	50% CBR	80%	(40.09%, 59.91%)
B2	N=20	20% CBR	80%	(9.02%, 36.07%)

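### Does Table 13 give Cohort A the wrong 80% interval for its stated 15% response rate?

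*Combined protocol and SAP*

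**What the plan says.** Section 15.2.2 sets a different benchmark for each Phase IIa population. For Cohort A (ESR1-mutant disease, planned N=30) it prefers ORR to clinical benefit rate (CBR) and treats as of interest a rate of "confirmed complete and/or partial responses of at least 15% (5 out of 30 patients"). For B1 and B2 it names desired observed CBRs of 50% and 20%.

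Table 13, "Two-Sided Confidence Intervals for Phase IIa Cohorts", follows directly. At the 80% level it prints:

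| Cohort | N | Assumed observed effect | Interval |
|---|---|---|---|
| A | 30 | 15% ORR | 8.34% to 28.74% |
| B1 | 50 | 50% CBR | 40.09% to 59.91% |
| B2 | 20 | 20% CBR | 9.02% to 36.07% |

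The table does not name the interval method. Section 15.1 says that "no confirmatory inferential analyses are planned". Section 15.5 asks only that ORR and CBR be summarized by dose level and cohort.

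**The concern.** The labels for B1 and B2 correspond to whole numbers of patients (25 of 50 and 4 of 20). The Cohort A label does not: 0.15 × 30 = 4.5. A reader who takes the row at face value and recomputes the interval for 15% at N=30 will not get the printed limits. The natural suspicion is that the interval is wrong, or that it was computed for another sample size or by another method.

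The row matters because it shows how precisely the response rate would be known at the very result said to justify taking the drug further in ESR1-mutant disease. A wrong interval there would misstate what 30 patients can show.

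**Working it through.** **Inputs.** N, labels, the 80% two-sided level and the printed limits come from Table 13. The count of 5 in 30 comes from section 15.2.2. The interval method is not stated, so it is identified first from the rows whose counts are not in doubt.

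**Formula.** For x responders in n, the exact (Clopper-Pearson) interval at 80% has

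- lower limit = 10th percentile of Beta(x, n − x + 1)
- upper limit = 90th percentile of Beta(x + 1, n − x)

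**Step 1: identify the method from B1 and B2.**

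- B1, 25/50: Beta(25, 26) and Beta(26, 25) give 40.09% and 59.91%, as printed.
- B2, 4/20: Beta(4, 17) and Beta(5, 16) give 9.02% and 36.07%, as printed.

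**Step 2: apply it to Cohort A with the count in the text.**

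- 5/30 = 16.67%: Beta(5, 26) and Beta(6, 25) give 8.34% and 28.74%, as printed.

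All three rows therefore come from one method, and the Cohort A input was 5 responders.

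**Step 3: see whether the label itself could have been the input.** With 15% at N=30 (a notional 4.5 responders):

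| Method | 80% interval |
|---|---|
| Clopper-Pearson formula, x = 4.5 | 7.12% to 26.83% |
| Wilson | 8.48% to 25.15% |
| Wald | 6.65% to 23.35% |
| Jeffreys | 8.34% to 24.90% |
| Printed | 8.34% to 28.74% |

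None gives the printed pair. The Jeffreys lower limit agrees only because Jeffreys at x = 4.5 uses the same Beta(5, 26) as the exact lower limit for 5/30; its upper limit does not agree. Continuity-corrected Wilson and Wald, Agresti-Coull, and exact intervals at 90% or 95% also fail. A search over N from 24 to 36 and counts from 2 to 8 found only 5/30 with the exact method.

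**Step 4: check the threshold against the count.**

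- 4/30 = 13.3%, below 15% (exact interval 5.94% to 24.90%)
- 5/30 = 16.7%, at or above 15%

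Five is the smallest count that meets a rate of at least 15%, so the text of section 15.2.2 agrees with itself and with the interval.

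**Size of the mismatch.** 16.7 − 15.0 = 1.7 percentage points, in one label.

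**The case for a change.** The strongest case for acting is that the column is headed as an assumed observed effect, not a threshold. In the other two rows the label is exactly the proportion behind the interval; in Cohort A it is not. Nor is this rounding: 16.7% does not round to 15%, and the same row prints its limits to two decimals. With no method named, someone working from the table alone could conclude that a correct interval is faulty. Relabelling one cell would cost almost nothing.

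The inconsistency in the label stands; the consequence does not. The count sits in the same subsection, just above the table, so a reader of 15.2.2 has everything needed: 5, 30 and 80%. Comparing the printed upper limit with intervals for 4.5 responders shows that 15% was not the input. It does not show that the limit is too high, since 4.5 responders cannot occur.

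One might also ask whether Cohort A ended at 30. The documents do not say. Section 7.2 allows Cohort A1 to close early "After enrollment is complete in Cohorts A2, B1, and B2 of the Phase IIa portion of the study", and section 1.1 gives only a combined count for Phase IIa and Cohort D1. That does not affect a planning table. The benchmark count is also stable: 0.15 × 27 = 4.05 and 0.15 × 33 = 4.95, so five is the smallest passing count for any size from 27 to 33.

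**Conclusion.** The concern is right about the label and wrong as a reason to change the plan. The Cohort A interval in Table 13 is the correct exact 80% interval for 5/30, the result that section 15.2.2 names as the benchmark. The label repeats the 15% threshold where the rate behind the interval is 16.7%, a clerical looseness of 1.7 points.

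The sample size, interval, count and threshold would all stay as they are after any relabelling. The table illustrates precision at the planning stage; it is not an analysis rule. Phase IIa enrollment is complete, the analyses are descriptive, and the sponsor has halted development of the drug. Nothing the trial does or can conclude depends on this cell.

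This rests on one inference: that the unnamed method is Clopper-Pearson. All six printed limits agree with it to two decimals, which leaves little room for doubt.

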**Table 13 Two-Sided Confidence Intervals for Phase IIa Cohorts**

Cohort	Sample Size	Assumed Observed Effect	Confidence Level	Two-sided CI
A	N=30	15% ORR	80%	(8.34%, 28.74%)
B1	N=50	50% CBR	80%	(40.09%, 59.91%)
B2	N=20	20% CBR	80%	(9.02%, 36.07%)

### **15.2.3 Phase Ib**

Approximately 5 patients *have been* enrolled in the Phase Ib dose escalation cohorts (Cohorts C0 and C1). *No additional patients will be enrolled.*

Because the dose escalation portion of Phase Ib follows the same dose escalation rules as the Phase Ia, the probability of escalation from dose level C1 to dose level C2 is also shown in [Table 11](#). Similarly, the probability of failing to observe toxicity in dose

escalation cohorts (Cohorts C0 and C1) and safety run-in cohort (Cohort D1) is shown in [Table 14](#).

Approximately 4 patients *have been* enrolled at the RP2D of GDC-0810 and palbociclib, and approximately 6 patients *have been* enrolled at 600 mg of GDC-0810 and an LHRH agonist. With 10 patients, there is a 80% probability of observing an adverse event with a true underlying probability of 15%.

**Table 14 Probability of Safety-Signal Detection with 10 Patients**

True Underlying Probability of an AE (%)	Probability of Observing at Least 1 AE in 10 Patients (%)
5	40
10	65
15	80
20	89

## **15.3 SAFETY ANALYSES**

For safety analyses, the analysis population will include all enrolled patients who receive at least one dose of study medication.

Study treatment discontinuation and reasons for patient discontinuations from the study will be described and summarized. Study drug administration data will be listed and any dose modifications will be flagged.

### **15.3.1 Adverse Events**

Adverse events will be graded according to the NCI CTCAE v4.0 and coded to preferred term and system organ class (SOC).

All adverse events reported during the adverse event reporting period will be considered as treatment-emergent adverse events. Incidence rates will be summarized with frequency and percentage by MedDRA SOC and preferred term, with all patients treated as the denominator, unless otherwise specified. In addition, adverse event incidence rates will also be summarized by severity and relationship to study drug.

Treatment-related adverse events are those judged by the Investigator to be at least possibly related to the study drug. Patients with multiple occurrences of events will only be counted once at the maximum severity attributed to study drug for each preferred term, SOC, and overall.

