At 600 mg by mouth (PO) daily under nonfasting conditions, GDC-0810 was well tolerated. The associated adverse events were largely Grade 1, without need for any dose holds, dose reductions or permanent study drug discontinuations. Diarrhea was the most frequently reported adverse event, occurring in all 6 patients at the 600-mg QD nonfasting dose level (5 patients with Grade 1 and 1 patient with Grade 2 diarrhea), with 2 patients receiving loperamide, and 4 patients not requiring any anti-diarrheal agents. The RP2D chosen for this study is 600 mg PO QD under fed conditions (within 30 minutes after a meal). Based on the nonclinical findings and preliminary clinical findings, the following additional potential safety risks have been highlighted: uterotrophic effects (i.e., endometrial thickening and polyps), VTE effects (e.g., pulmonary embolism, deep vein thrombosis), kidney dysfunction (animal models only), phototoxicity (in-vitro model only), and drug-drug interaction with CYP2C9 substrates (in-vitro model only).

Specific eligibility criteria designed to minimize risk of GI toxicity and other potential risks are included in Section 7, and robust safety monitoring and risk mitigation strategies for all expected or potential safety risks are described in Section 10.4. The implementation of appropriate dose-modification and treatment guidelines, appropriate choice of inclusion/exclusion criteria, real-time safety monitoring and assessments, and periodic assessment of aggregate safety data and risk/benefit ratio combine to form the monitoring and risk mitigation system.

In summary, the GDC-0810 safety profile remains acceptable and clinical benefit has been observed in patients with refractory ER+ (HER2-) breast cancer.

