**Cohort B2 only:** Prior fulvestrant allowed

- At least 2 weeks must have elapsed from the use of the most recent endocrine therapy (for Cohort A1, if most recent endocrine therapy is tamoxifen, see inclusion criterion above)
- At least 3 weeks must have elapsed from the use of any chemotherapy
- Females, 18 years of age or older
- Postmenopausal status defined as:

Prior bilateral surgical oophorectomy

Age  $\geq$  56 years: natural amenorrhea with  $\geq$  1 year since last menses

Age  $<$  56 years with amenorrhea  $\geq$  1 year since last menses and serum estradiol levels ( $<$  20 pg/mL) and FSH levels ( $>$  40 mIU/mL) in the postmenopausal range

Age <56 years who had hysterectomy with one or both ovaries left in place, or with tamoxifen-induced amenorrhea together with a tamoxifen discontinuation of  $\geq 1$  year and serum estradiol levels (<20 pg/mL) and FSH levels (>40 mIU/mL) in the postmenopausal range

Age <56 years who have medical menopause, such as LHRH agonist (on stable dose  $\geq 1$  year) with amenorrhea  $\geq 1$  year since last menses and serum estradiol levels in the postmenopausal range (<20 pg/mL) irrespective of FSH/LH levels. Cause of medical menopause should be discussed with the Medical Monitor.

- ECOG performance status 0 or 1
- Resolution of all acute toxic effects of prior therapy or surgical procedures to baseline or Grade  $\leq 1$  (except alopecia or other toxicities not considered to be a safety risk for the patient)
- Adequate organ function as defined by the following criteria:
  - Absolute neutrophil count (ANC)  $\geq 1500/\mu\text{L}$
  - Platelets  $\geq 100,000/\mu\text{L}$
  - Serum aspartate transaminase (AST) and serum alanine transaminase (ALT)  $\leq 3 \times \text{ULN}$ , or AST and ALT  $\leq 5 \times \text{ULN}$  if liver function abnormalities are due to underlying malignancy or liver metastasis
  - Total serum bilirubin  $\leq 1.5 \times \text{ULN}$  regardless of liver involvement secondary to tumor. Inclusion of patients with increased serum indirect bilirubin ( $\leq 3 \times \text{ULN}$ ) due to Gilbert's syndrome is permitted
  - Serum creatinine  $\leq 1.5 \times \text{ULN}$
  - QTc  $\leq 460$  msec
- Signed and dated informed consent document indicating that the subject has been informed of all the pertinent aspects of the trial prior to enrollment
- Willingness and ability to comply with scheduled visits, treatment plan, laboratory tests, and other trial procedures

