### **8.2.2 Phase IIa Exclusion Criteria**

- Untreated or symptomatic CNS metastases.

Note: Patients with treated and asymptomatic CNS metastases that are radiographically stable within 12 weeks prior to enrollment will be allowed, provided long-term use of corticosteroids have been discontinued within 4 weeks prior to enrollment

- Patients with a history of endometrial polyps, endometrial cancer, atypical endometrial hyperplasia, or other significant endometrial disorders should be excluded unless they have undergone total hysterectomy and there is no evidence of active disease.
- Prior treatments:

EXCLUSIONS	Prior Endocrine Therapy	Prior Chemotherapy
Cohort A1	▪ Fulvestrant	▪ > 1 prior chemotherapy in the advanced/metastatic setting
Cohort A2		▪ > 1 prior chemotherapy in the advanced/metastatic setting
Cohort B1	▪ > 1 prior AI in the advanced/metastatic setting ▪ Fulvestrant	▪ Prior chemotherapy in the advanced/metastatic setting (prior adjuvant chemotherapy is allowed so long as it occurred $\geq$ 12 months prior to enrollment)
Cohort B2	▪ > 1 prior AI in the advanced/metastatic setting	▪ > 1 prior chemotherapy in the advanced/metastatic setting

- Current treatment with any systemic anti-cancer therapies for advanced disease
- Diagnosis of any secondary malignancy within 2 years prior to enrollment, except for adequately treated basal cell or squamous cell skin cancer, or carcinoma in situ

- Any of the following within 12 months prior to enrollment: myocardial infarction, severe/unstable angina, ongoing cardiac dysrhythmias of Grade  $\geq 2$ , atrial fibrillation of any grade, coronary/peripheral artery bypass graft, symptomatic congestive heart failure, or cerebrovascular accident including transient ischemic attack
- Active inflammatory bowel disease (e.g. Crohn's disease or ulcerative colitis), any active bowel inflammation (including diverticulitis), chronic diarrhea, short bowel syndrome, or history of upper gastrointestinal surgery including gastric resection
- Known human immunodeficiency virus infection
- Known clinically significant history of liver disease consistent with Child-Pugh Class B or C, including active viral or other hepatitis (e.g., Hepatitis B or Hepatitis C virus), current alcohol abuse, or cirrhosis
- Major surgery within 4 weeks prior to enrollment
- Radiation therapy within 2 weeks prior to enrollment

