### **11.1.9 Endometrial Thickness Assessments (if applicable)**

*To assess for any potential effect of *study treatment* on the uterus, transvaginal ultrasound scans will be performed to monitor endometrial thickness *at screening, the study drug discontinuation visit, and as clinically indicated*. Transvaginal ultrasounds are not required for patients who have had a hysterectomy.*

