#### **Adverse Events of Interest**

- DLTs occurring during the DLT assessment window
- Grade  $\geq 2$  vomiting/diarrhea

- Grade  $\geq$  3 nausea
- Grade  $\geq$  2 thromboembolic events (including pulmonary embolism)
- Grade  $\geq$  2 vaginal or uterine hemorrhage
- Grade  $\geq$  3 elevation of ALT or AST

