14. Tumor Biopsies: All Cohort A patients with safely accessible soft tissue and/or visceral metastases will have tumor biopsies performed at Screening, at Cycle 2 (Day 8 for patients in Cohort A1), and if feasible, at the time when disease progression is suspected (especially if disease progression occurs prior to Cycle 3). Biopsies should be collected during the period between $\geq$ 2 and $\leq$ 12 hours postdose. Tumor Biopsies are optional but strongly encouraged for Cohort B patients with safely accessible soft tissue and/or visceral metastases.
15. Archival paraffin-embedded tissue may be collected to evaluate the histology of the tumor. If fresh tumor tissue biopsy cannot be obtained at screening, every reasonable effort should be made to obtain the most recent archival tissue sample. Tumor blocks are preferred, but in the event that local regulations prevent the shipment of tumor blocks, 15-20 unstained, serially cut slides are requested. Minimum tissue requirements are further described in the laboratory manual. Cytological, fine-needle aspiration, and decalcified bone biopsy samples are not acceptable.
16. Adverse Events and Concomitant Medications/Treatments: Patients must be followed for adverse events and associated concomitant medications and treatments on a monthly basis, from the first day of study treatment until at least 28 days after the last dose of study treatment, or until all serious or study drug-related toxicities have resolved or are determined to be "chronic" or "stable", whichever is later.
17. Transvaginal Ultrasound (if applicable): Assessment of endometrial thickness will be performed at Screening, at the end of treatment (if treated for at least 2 cycles), and as clinically indicated. Any abnormal bleeding should be evaluated with a complete gynecological workup.
18. Study Drug Compliance: GDC-0810 bottle(s) including any unused capsules should be brought to each clinic visit for drug accountability.

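### Uterine and endometrial adverse event rates are divided by all treated patients, including women without a uterus, which understates the rate among women at risk by the hysterectomy share

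*Combined protocol and SAP*

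**What the plan says.** Section 15.3 defines the safety population without any anatomical condition: "the analysis population will include all enrolled patients who receive at least one dose of study medication". Section 15.3.1 then gives incidence "by MedDRA SOC and preferred term, with all patients treated as the denominator, unless otherwise specified". The closing words of that sentence leave room for other denominators, but no section supplies one for uterine, endometrial or vaginal bleeding terms.

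Women without a uterus can enter by two routes, which appear in the criteria for all three phases. The definition of postmenopausal status includes younger women "who had hysterectomy with one or both ovaries left in place" (8.2.1). Women with a history of endometrial disease "should be excluded unless they have undergone total hysterectomy and there is no evidence of active disease" (8.2.2). Section 11.1.9 recognises that these women have nothing to scan: "Transvaginal ultrasounds are not required for patients who have had a hysterectomy".

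The uterus is a stated safety topic. Section 3 lists "uterotrophic effects (i.e., endometrial thickening and polyps" among the potential risks, and Section 12.1.3 makes Grade 2 or higher "vaginal or uterine hemorrhage" immediately reportable. Section 15.3.5 plans a separate summary of change in measured endometrial thickness by visit. It sets no denominator for adverse events.

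**The concern.** An incidence proportion estimates risk only if everyone in the denominator could have the event. For endometrial thickening, polyps, hyperplasia, endometrial cancer and uterine bleeding, a woman after hysterectomy could not, yet she is counted as a patient treated without the event.

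The error goes one way: the percentage is too low for the women who carry the risk. It also varies with case mix. Section 15.1 summarises data by phase and dose cohort, so two cohorts with the same risk among women with a uterus would show different percentages if their hysterectomy shares differ. Safety is part of the primary objective in Phases Ia and Ib and a secondary objective in Phase IIa, so a highlighted potential risk should be reported on a denominator that means what it appears to mean.

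**Working it through.** **The plan's own figure.** The documents report no uterine or endometrial event rate. The nearest figure on a whole-study denominator is in Section 1.1: 9 venous thromboembolic events with a combined n of 148. 9/148 = 6.08%, which matches the stated 6.1%. For that event every treated patient is at risk, so the denominator is sound.

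**Inputs.**
- Denominator: all treated patients (15.3.1).
- h, the share of treated patients without a uterus: not in the documents. Assumed to be 10% to 40%, and shown as a range.
- Illustration: 5 events in 100 treated patients. The 100 is the Phase IIa size (15.2.2); the 5 is assumed.
- Endometrial cancers to date: 0 (1.1). The 148 is the combined n that Section 1.1 gives for other events, used here for the whole study.

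**Size of the understatement.** With N treated and x events, the reported rate is x/N and the rate among women at risk is x/[N(1 − h)]. So reported rate = at-risk rate × (1 − h), and the relative understatement is exactly h. It does not depend on x, provided x is at least 1.

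| h | Women with a uterus per 100 treated | 5 events: all treated | 5 events: women with a uterus | True at-risk rate of 10% is reported as |
|---|---|---|---|---|
| 10% | 90 | 5.0% | 5.6% | 9% |
| 20% | 80 | 5.0% | 6.25% | 8% |
| 30% | 70 | 5.0% | 7.1% | 7% |
| 40% | 60 | 5.0% | 8.3% | 6% |

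**Zero events.** The point estimate is 0% on either denominator, but the uncertainty is not the same. The one-sided 95% upper bound is 1 − 0.05^(1/n).
- All treated, n = 148: 2.0%.
- h = 10%, n = 133: 2.2%.
- h = 20%, n = 118: 2.5%.
- h = 30%, n = 104: 2.8%.
- h = 40%, n = 89: 3.3%.

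**Pooled hemorrhage event.** The event of special interest combines vaginal and uterine bleeding. Vaginal bleeding does not need a uterus, so all treated patients is the right denominator for that part. The correction applies only to the uterine part, which needs the two to be separated.

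**The case against.** All treated patients is the conventional denominator for adverse events, and 15.3.1 permits others where specified. The analysis is descriptive, with no confirmatory inference (15.1), and no stopping rule or hypothesis depends on this percentage. Enrollment has ended and development is halted. Uterotrophic effects are a potential risk; Section 1.1 names only diarrhea, vomiting and nausea as identified risks. Section 15.3.5 already covers measured thickness: a change from baseline needs two scans, and 15.1 rules out imputation, so women without a uterus drop out there. All of this stands. It limits the importance of the point and is a reason to keep the all-treated column. It does not give polyps, hyperplasia, endometrial cancer, uterine bleeding or thickening reported as an adverse event a suitable denominator.

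Two stronger readings are tempting, and the documents do not support them.

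A reader might infer a second layer of dilution from missing scans. Under Appendix 2, "Assessment of endometrial thickness will be performed at Screening, at the end of treatment (if treated for at least 2 cycles), and as clinically indicated", so women treated for less than 2 cycles may have no post-baseline scan. But dividing by scanned women only is not a bias correction. On that rule, unscanned women had shorter exposure and need not share the risk of the others, and scans done on clinical indication follow symptoms, so a scanned-only percentage can overstate the risk. The scanned share is not stated either.

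A reader might also infer that a diluted rate led the amendment to drop the six-monthly ultrasounds. The amendment rationale does cite a low event rate, but it also cites alignment with another GDC-0810 study, keeps the end-of-treatment scan, and does not say which events or denominator it used.

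**Conclusion.** The point holds for the hysterectomy share alone. Given the eligibility rules and the single denominator, the rate of uterine and endometrial events among women at risk is understated by h whenever at least one treated woman lacks a uterus and at least one event occurs. The direction follows from the documents; the size does not, because h is not reported. Over the assumed 10% to 40%, the at-risk rate is 1.11 to 1.67 times the reported one. With no events, only the upper bound moves.

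No decision in the plan depends on this, so it is a modest reporting weakness. It is worth correcting because it concerns a risk that the protocol itself highlights, and because the data should already be at hand.

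**What to change.** Add to Section 15.3.1: *For uterine and endometrial preferred terms (endometrial thickening, polyp, hyperplasia, endometrial cancer, uterine hemorrhage), the percentage among treated patients with a uterus at baseline is reported beside the percentage among all treated patients, with both denominators shown. Vaginal hemorrhage is tabulated separately from uterine hemorrhage and uses all treated patients. For findings detected by transvaginal ultrasound, the number of patients with at least one post-baseline scan is given as context.*

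The scan count describes how far such findings were looked for and should not be presented as a corrected rate. Surgeries are recorded at screening (11.1.2), so uterus status should be recoverable without new data; patients whose status cannot be established should be counted and shown. The halt to enrollment is no obstacle, since only the analysis changes.

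The cost is one extra denominator in one table, the split of the pooled hemorrhage event, and slightly less favourable percentages.
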